11.7. Appendix 7: Values of Potential Clinical Importance

11.7.1. Laboratory Values

| Haematology | | | | |
|------------------------------|----------------------|------------------|----------------|----------------|
| Laboratory Parameter | Units | Category | Clinical Con | cern Range |
| | | | Low Flag (< x) | High Flag (>x) |
| | | Male | | 0.54 |
| Hematocrit | Ratio of 1 | Female | | 0.54 |
| | | Δ from BL | ↓0.075 | |
| | ~/I | Male | | 180 |
| Hemoglobin | g/L | Female | | 180 |
| | | Δ from BL | ↓25 | |
| Lymphocytes | x10 ⁹ / L | | 0.8 | |
| Neutrophil Count | x10 ⁹ / L | | 1.5 | |
| Platelet Count | x10 ⁹ / L | | 100 | 550 |
| While Blood Cell Count (WBC) | x109/ L | | 3 | 20 |
| [Insert as Required] | [Units] | | | |

| Clinical Chemistry | | | | |
|----------------------|--------|------------------|------------------------|----------------|
| Laboratory Parameter | Units | Category | Clinical Concern Range | |
| | | | Low Flag (< x) | High Flag (>x) |
| Albumin | mmol/L | | 30 | |
| Calcium | mmol/L | | 2 | 2.75 |
| Creatinine | mmol/L | Δ from BL | | ↑ 44.2 |
| Glucose | mmol/L | | 3 | 9 |
| Potassium | mmol/L | | 3 | 5.5 |
| Sodium | mmol/L | | 130 | 150 |

| Liver Function | | | | |
|----------------|--------|----------|------------------------|--|
| Test Analyte | Units | Category | Clinical Concern Range | |
| ALT/SGPT | U/L | High | ≥ 2x ULN | |
| AST/SGOT | U/L | High | ≥ 2x ULN | |
| AlkPhos | U/L | High | ≥ 2x ULN | |
| T Bilirubin | µmol/L | High | ≥ 1.5xULN | |

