7.3. Clinical Laboratory Analyses

Laboratory results will be included in the reporting of this study for hematology, coagulation, clinical chemistry, and urinalysis.

Protocol-specified clinical laboratory tests will be summarized using descriptive statistics. The statistics will be presented for each scheduled assessment during the study and change from baseline to each scheduled assessment. Presentations will use SI Units, as provided by the labs or converted from values in other units. Clinical laboratory data collected during unscheduled visits of study conduct that were not required per protocol, such as for special testing to evaluate an AE, will be listed and not summarized.

Based upon laboratory normal ranges, the laboratory test results will be categorized according to the normal range as low (below the lower limit), normal (within the normal range) and high (above the upper limit). Summary statistics for change from baseline based on PCI will also be tabulated. The details of the planned displays are in Appendix 11: List of Data Displays.

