11.8. Appendix 8: Pop PK Dataset Specification

For the purpose of population PK analysis, the raw plasma concentration data in the systemic PK population (including all the available plasma concentration data) will be merged for each individual with the following demographic and baseline/screening variables where available. In addition, the 12-ECG data as listed below will be merged with plasma concentration data by the planned time.

The dataset will be a comma delimited ASCII text file, named as: NM.205822.PK.v1.csv.

| Variable | Description | Format | Unit | Missing | Note |
|----------|-------------------------------------|---------|------------|---------|--|
| AGE | Subject Age | Num | Specify | -99 | From source data. |
| SEX | Subject gender | Integer | None | Never | 0=Male, 1=Female |
| SEXTEXT | Subject gender text | Char | None | Never | Text corresponding to code for SEX |
| BMI | Baseline Body Mass Index | Num | Specify | -99 | From source data. Formula: Weight(kg)/(height(m)**2) |
| WT | Baseline Subject weight | Num | Specify | -99 | From source data. |
| HT | Baseline Subject height | Num | Specify | -99 | From source data. |
| RACE | Subject race code1 | Integer | None | -99 | From source data e.g. 1=African American / African Heritage 2=American Indian or Alaska Native 3=Asian – Central / South Asian Heritage 4=Asian – East Asian Heritage 5=Asian – Japanese Heritage 6=Asian – South East Asian Heritage 7=Asian – Mixed Race 8=Native Hawaiian or other Pacific Islander 9=White – Arabic / North African Heritage 10=White – White / Caucasian / European Heritage 11=White – Mixed Race 12=Mixed Race |
| RACETXT | Subject race text | Char | None | Never | Text corresponding to code for RACE |
| ETHN | Subject ethnicity | Num | None | -99 | From source data definition. E.g 1=Hispanic or Latino, 2=Non-Hispanic |
| ETHNTEXT | Subject ethnicity text | Char | None | Never | Text corresponding to code for ETHN. |
| SCR | Serum Creatinine | Num | micromol/L | -99 | Baseline/screening defined in the source dataset |
| CRCL | Baseline Creatinine Clearance | Num | mL/min | -99 | From source data. formula e.g. Creatinine Clearance will be calculated based on the Cockcroft-Gault equation. • CrCL (ml/min) = [140 – AGE (in years)]*Weight(kg)*0.85 (for female patients) / [72* Serum Creatinine (micromol/L) * 0.0113 |
| ALT | Alanine aminotransferase | Num | | -99 | Baseline/screening defined in the source dataset |

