| AST | Aspartate aminotransferase | Num | | -99 | Baseline/screening defined in the source dataset |
| ALB | Albumin | Num | | -99 | Baseline/screening defined in the source |

| Variable | Description | Format | Unit | Missing | Note |
|----------|--|--------|------|---------|---|
| | | | | | dataset |
| TBIL | Total bilirubin | Num | | -99 | Baseline/screening defined in the source dataset |
| ECGTM | Clock time of ECG recording in hours | Num | | | ECGTM should be calculated as: hr + min/60 e.g. if clock time of ECG recording is 09:30, then ECGTM= 9 + 30/60= 9.5 |
| HR | Heart rate in bpm | Num | bpm | | As in source dataset |
| HRBL | Baseline heart rate in bpm | Num | bpm | | As in source dataset |
| PR | PR interval in ms | Num | ms | | As in source dataset |
| PRBL | Baseline corresponding PR interval in ms | Num | ms | | As in source dataset |
| QRS | QRS complex duration in ms | Num | ms | | As in source dataset |
| QRSBL | Baseline corresponding QRS interval in ms | Num | ms | | As in source dataset |
| QT | Uncorrected QT interval in ms | Num | ms | | As in source dataset |
| QTBL | Baseline uncorrected QT interval in ms | Num | ms | | As in source dataset |
| QTcF | QT with Fridericia's correction in ms | Num | ms | | As in source dataset |
| QTcFBL | Baseline QT with Fridericia's correction in ms | Num | ms | | As in source dataset |
| RR | RR interval in ms | Num | ms | | As in source dataset |
| RRBL | Baseline corresponding RR interval in ms | Num | ms | | As in source dataset |

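### Appendix 7 labels the creatinine and albumin flags of potential clinical importance in mmol/L; if the limits are applied with those units, the chemistry PCI counts are wrong

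*SAP*

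**What the plan says.** The clinical chemistry table in SAP section 11.7.1 has six analytes, all with the unit mmol/L. Two rows matter here:

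- Creatinine, labelled "Creatinine | mmol/L" and flagged on change from baseline: "Creatinine | mmol/L | Δ from BL | | ↑ 44.2".
- Albumin, flagged low: "Albumin | mmol/L | | 30".

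Appendix 8 (section 11.8), which specifies the population PK dataset, defines creatinine as "Serum Creatinine | Num | micromol/L". Its creatinine-clearance formula uses "Serum Creatinine (micromol/L) * 0.0113" in the denominator. For albumin the same appendix leaves the unit cell empty: "ALB | Albumin | Num | | -99".

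Section 7.3 gives the general rule on laboratory units: "Presentations will use SI Units, as provided by the labs or converted from values in other units". It names no unit for either analyte. Note 2 to Table 3 in section 7 says that chemistry summaries will include results by PCI criteria. Tables 3.22 to 3.24 (Part 1, Part 2, bystanders) are the displays that do this.

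**The concern.** Within one document, creatinine appears on two scales that differ by a factor of 1000. The number in Appendix 7 fits the scale of Appendix 8, not its own label. The albumin limit looks wrong for a similar reason: 30 is an unremarkable number in g/L but a very large one in mmol/L.

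The label does not look like a lost symbol. The liver function table in the same section prints µmol/L for bilirubin. The same unit runs down the whole chemistry column, and it raises no question for calcium, glucose, potassium or sodium.

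At stake are the PCI counts in Tables 3.22 to 3.24. Section 2.2 lists clinical laboratory assessments among the primary safety endpoints. ECG and vital signs each have a listing of participants with PCI values (Listings 55 to 57 and 65 to 67), but chemistry has none, so these three tables are its only PCI display. A creatinine row that can only read zero could be taken as reassurance about renal function.

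**Working it through.** **Inputs from the SAP**
- Creatinine limit: rise of 44.2, labelled mmol/L (section 11.7.1).
- Albumin limit: below 30, labelled mmol/L (section 11.7.1).
- Creatinine unit elsewhere: micromol/L, with the factor 0.0113 in the clearance formula (section 11.8). I read this factor as the conversion from micromol/L to mg/dL.

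**Inputs assumed, not in the SAP**
- Baseline creatinine: 60 to 110 micromol/L.
- Molar mass of albumin: 60 to 70 kDa, central value 66.5.
- Albumin values that might be seen: 20 to 60 g/L.

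The SAP states its limits without deriving them, so there is no figure of its own to reproduce.

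**Creatinine as labelled (mmol/L)**
- 44.2 mmol/L × 1000 = 44,200 micromol/L.
- 44,200 × 0.0113 = 499 mg/dL.
- Fold rise needed from a baseline of 60: (60 + 44,200) / 60 = 738.
- Fold rise needed from a baseline of 110: (110 + 44,200) / 110 = 403.
- Even a post-dose value of 2,000 micromol/L is a change of at most 2.0 mmol/L, far below 44.2. The flag cannot fire.

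**Creatinine read in the unit of Appendix 8 (micromol/L)**
- 44.2 × 0.0113 = 0.499 mg/dL. In reverse, 0.5 / 0.0113 = 44.2, so the limit corresponds to a round 0.5 mg/dL.
- Fold rise needed: (60 + 44.2) / 60 = 1.74, and (110 + 44.2) / 110 = 1.40. The flag can fire.

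**Albumin as labelled (mmol/L)**

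| Assumed molar mass (kDa) | 30 mmol/L in g/L | 20 g/L in mmol/L | 60 g/L in mmol/L |
|---|---|---|---|
| 60 | 30 × 60 = 1,800 | 0.33 | 1.00 |
| 66.5 | 30 × 66.5 = 1,995 | 0.30 | 0.90 |
| 70 | 30 × 70 = 2,100 | 0.29 | 0.86 |

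Every value from 20 to 60 g/L is at most 1.0 mmol/L, at least 30 times below the limit. Everyone is flagged low.

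**Albumin read in g/L**
- 30 g/L lies inside the assumed range of 20 to 60 g/L, so the flag can separate low values from the rest.

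**The case against.** The strongest reply is that the numbers are sound and only two labels are wrong. The stated consequences need someone to put the results on the mmol/L scale before applying the limits, and the SAP does not order that. Section 7.3 asks for SI units without naming one for either analyte. The only creatinine data unit in the SAP is micromol/L, although it is given for a different dataset. If a programmer compares 44.2 and 30 with data in micromol/L and g/L, both flags work. This stands, and it makes the harm conditional. It does not remove the defect, because the plan followed as written gives wrong counts, and an unrecorded correction leaves independent programming with nothing valid to check against.

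A reader might infer that a creatinine rise would go unseen in this trial. The SAP does not support that. Tables 3.19 to 3.21 summarise chemistry change from baseline by visit, Listings 41 to 43 give the individual chemistry data, and section 7.3 sorts results into low, normal and high by the laboratory's ranges. None of these uses the Appendix 7 units. Nor does the SAP tie any decision rule to the flag, and section 2.4 says that no hypothesis is tested.

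Two further points stand. The albumin half has no internal contradiction behind it and rests on outside assumptions. An albumin flag on every participant would also be noticed in the first draft table, so a silent miss is plausible for creatinine only.

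**Conclusion.** The unit labels in Appendix 7 should be fixed. The evidence differs between the two analytes:

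- **Creatinine:** the error is shown from the SAP alone. Appendix 7 and Appendix 8 differ by a factor of 1000, and the number fits the unit in Appendix 8.
- **Albumin:** the label is implausible rather than contradicted. The conclusion rests on an assumed molar mass and range of values, but it is the same throughout 60 to 70 kDa.

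If the limits are applied with the units as labelled, no participant is flagged for creatinine and all are flagged for albumin, in Tables 3.22 to 3.24 only. It would go too far to say that the creatinine limit itself is 1000 times too high, or that the flags will fail whatever is done: the numbers are not shown to be wrong, and the failure depends on following the label. Since other displays would still show a creatinine rise, this is a point to fix before reporting, not one that undermines the safety analysis.

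**What to change.** In section 11.7.1, leave 44.2 and 30 unchanged and correct two unit cells:

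- Creatinine: µmol/L, to match Appendix 8.
- Albumin: the unit in which the laboratory reports it, evidently g/L, to be confirmed from the laboratory transfer specification. Enter the same unit in the blank albumin cell in Appendix 8.

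Then check the programmed PCI limits against the units in the laboratory transfer before Tables 3.22 to 3.24 are produced. The cost is two cells in one table, one blank cell filled, and a short programming check. No clinical threshold, dataset or display changes.

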11.7.2. ECG

| ECG Parameter | Units | Clinical Concern Range | | |
|----------------------------|-------|------------------------|-------|--|
| | | Lower | Upper | |
| Absolute | | | | |
| Abaaluta OTa Intamial | | > 450 | <480 | |
| Absolute QTc Interval | msec | ≥ 480 | < 500 | |
| | | ≥ 500 | | |
| Absolute PR Interval | msec | < 110 | > 220 | |
| Absolute QRS Interval | msec | < 75 [| > 110 | |
| Change from Baseline | | | | |
| Increase from Baseline QTc | msec | > 30 | < 60 | |
| | msec | ≥ 60 | | |

11.7.3. Vital Signs

| Vital Sign Parameter | Units | Clinical Concern Range | | |
|--------------------------|-------|------------------------|-------|--|
| (Absolute) | | Lower | Upper | |
| Systolic Blood Pressure | mmHg | < 85 | > 160 | |
| Diastolic Blood Pressure | mmHg | < 45 | > 100 | |
| Heart Rate | bpm | < 40 | > 110 | |

| Vital Sign Parameter | Units | Clinical Concern Range | | |
|--------------------------|-------|------------------------|----------|--|
| (Change from Baseline) | | Decrease | Increase | |
| Systolic Blood Pressure | mmHg | ≥ 40 | ≥ 40 | |
| Diastolic Blood Pressure | mmHg | ≥ 20 | ≥ 20 | |
| Heart Rate | bpm | ≥ 30 | ≥ 30 | |

11.8. Appendix 8: Pop PK Dataset Specification

For the purpose of population PK analysis, the raw plasma concentration data in the systemic PK population (including all the available plasma concentration data) will be merged for each individual with the following demographic and baseline/screening variables where available. In addition, the 12-ECG data as listed below will be merged with plasma concentration data by the planned time.

The dataset will be a comma delimited ASCII text file, named as: NM.205822.PK.v1.csv.

| Variable | Description | Format | Unit | Missing | Note |
|----------|-------------------------------------|---------|------------|---------|--|
| AGE | Subject Age | Num | Specify | -99 | From source data. |
| SEX | Subject gender | Integer | None | Never | 0=Male, 1=Female |
| SEXTEXT | Subject gender text | Char | None | Never | Text corresponding to code for SEX |
| BMI | Baseline Body Mass Index | Num | Specify | -99 | From source data. Formula: Weight(kg)/(height(m)**2) |
| WT | Baseline Subject weight | Num | Specify | -99 | From source data. |
| HT | Baseline Subject height | Num | Specify | -99 | From source data. |
| RACE | Subject race code1 | Integer | None | -99 | From source data e.g. 1=African American / African Heritage 2=American Indian or Alaska Native 3=Asian – Central / South Asian Heritage 4=Asian – East Asian Heritage 5=Asian – Japanese Heritage 6=Asian – South East Asian Heritage 7=Asian – Mixed Race 8=Native Hawaiian or other Pacific Islander 9=White – Arabic / North African Heritage 10=White – White / Caucasian / European Heritage 11=White – Mixed Race 12=Mixed Race |
| RACETXT | Subject race text | Char | None | Never | Text corresponding to code for RACE |
| ETHN | Subject ethnicity | Num | None | -99 | From source data definition. E.g 1=Hispanic or Latino, 2=Non-Hispanic |
| ETHNTEXT | Subject ethnicity text | Char | None | Never | Text corresponding to code for ETHN. |
| SCR | Serum Creatinine | Num | micromol/L | -99 | Baseline/screening defined in the source dataset |
| CRCL | Baseline Creatinine Clearance | Num | mL/min | -99 | From source data. formula e.g. Creatinine Clearance will be calculated based on the Cockcroft-Gault equation. • CrCL (ml/min) = [140 – AGE (in years)]*Weight(kg)*0.85 (for female patients) / [72* Serum Creatinine (micromol/L) * 0.0113 |
| ALT | Alanine aminotransferase | Num | | -99 | Baseline/screening defined in the source dataset |
| AST | Aspartate aminotransferase | Num | | -99 | Baseline/screening defined in the source dataset |
| ALB | Albumin | Num | | -99 | Baseline/screening defined in the source |

| Variable | Description | Format | Unit | Missing | Note |
|----------|--|--------|------|---------|---|
| | | | | | dataset |
| TBIL | Total bilirubin | Num | | -99 | Baseline/screening defined in the source dataset |
| ECGTM | Clock time of ECG recording in hours | Num | | | ECGTM should be calculated as: hr + min/60 e.g. if clock time of ECG recording is 09:30, then ECGTM= 9 + 30/60= 9.5 |
| HR | Heart rate in bpm | Num | bpm | | As in source dataset |
| HRBL | Baseline heart rate in bpm | Num | bpm | | As in source dataset |
| PR | PR interval in ms | Num | ms | | As in source dataset |
| PRBL | Baseline corresponding PR interval in ms | Num | ms | | As in source dataset |
| QRS | QRS complex duration in ms | Num | ms | | As in source dataset |
| QRSBL | Baseline corresponding QRS interval in ms | Num | ms | | As in source dataset |
| QT | Uncorrected QT interval in ms | Num | ms | | As in source dataset |
| QTBL | Baseline uncorrected QT interval in ms | Num | ms | | As in source dataset |
| QTcF | QT with Fridericia's correction in ms | Num | ms | | As in source dataset |
| QTcFBL | Baseline QT with Fridericia's correction in ms | Num | ms | | As in source dataset |
| RR | RR interval in ms | Num | ms | | As in source dataset |
| RRBL | Baseline corresponding RR interval in ms | Num | ms | | As in source dataset |

11.9. Appendix 9: Abbreviations & Trade Marks

11.9.1. Abbreviations

| Abbreviation | Description |
|----------------------------------|--|
| ADaM | Analysis Data Model |
| AE | Adverse Event |
| AIC | Akaike's Information Criteria |
| A&R | |
| CDISC | Analysis and Reporting |
| CDISC | Clinical Data Interchange Standards Consortium Confidence Interval |
| | |
| CPMS | Clinical Pharmacology Modelling & Simulation |
| CS | Clinical Statistics |
| CSR | Clinical Study Report |
| CTR | Clinical Trial Register |
| CV _b /CV _w | Coefficient of Variation (Between) / Coefficient of Variation (Within) |
| DBF | Database Freeze |
| DBR | Database Release |
| DOB | Date of Birth |
| DP | Decimal Places |
| eCRF | Electronic Case Record Form |
| EMA | European Medicines Agency |
| FDA | Food and Drug Administration |
| FDAAA | Food and Drug Administration Clinical Results Disclosure Requirements |
| GSK | GlaxoSmithKline |
| IA | Interim Analysis |
| ICH | International Conference on Harmonization |
| IDMC | Independent Data Monitoring Committee |
| IDSL | Integrated Data Standards Library |
| IMMS | International Modules Management System |
| IP | Investigational Product |
| ITT | Intent-To-Treat |
| MMRM | Mixed Model Repeated Measures |
| PCI | Potential Clinical Importance |
| PD | Pharmacodynamic |
| PDMP | Protocol Deviation Management Plan |
| PK | Pharmacokinetic |
| PP | Per Protocol |
| PopPK | Population PK |
| QC | Quality Control |
| QTcF | Frederica's QT Interval Corrected for Heart Rate |
| QTcB | Bazett's QT Interval Corrected for Heart Rate |
| RAP | Reporting & Analysis Plan |
| RAMOS | Randomization & Medication Ordering System |
| SAC | Statistical Analysis Complete |
| SDSP | Study Data Standardization Plan |
| 0001 | Stady Data Standardization Filan |

| Abbreviation | Description |
|--------------|------------------------------|
| SDTM | Study Data Tabulation Model |
| SoA | Schedule of Activities |
| SOP | Standard Operation Procedure |
| TA | Therapeutic Area |
| TFL | Tables, Figures & Listings |

11.9.2. Trademarks

| Trademarks of the GlaxoSmithKline Group of Companies |
|---|
| ADVAIR |
| SAS |
| SigmaPlot |
| WinNonlin |

| Trademarks not owned by the GlaxoSmithKline Group of Companies |
|--|
| NONMEM |

11.10. Appendix 10: List of Data Displays

11.10.1. Data Display Numbering

The following numbering will be applied for RAP generated displays:

| Section | Tables | Figures | |
|------------------------------------|-------------|-------------|--|
| Study Population | 1.1 to 1.30 | N/A | |
| Efficacy | N/A | N/A | |
| Safety | 3.1 to 3.60 | N/A | |
| Pharmacokinetic | 4.1 to 4.7 | 4.1 to 4.12 | |
| Population Pharmacokinetic (PopPK) | N/A | N/A | |
| Pharmacodynamic and / or Biomarker | N/A | N/A | |
| Pharmacokinetic / Pharmacodynamic | N/A | N/A | |
| Section | List | ings | |
| ICH Listings | 1 to | 66 | |
| Other Listings | 66 to 82 | | |

11.10.2. Mock Example Shell Referencing

Non IDSL specifications will be referenced as indicated and if required example mock-up displays provided in Appendix 11: Example Mock Shells for Data Displays.

| Section | Figure | Table | Listing |
|------------------|---------|---------|---------|
| Study Population | POP_Fn | POP_Tn | POP_Ln |
| Safety | SAFE_Fn | SAFE_Tn | SAFE_Ln |
| Pharmacokinetic | PK_Fn | PK_Tn | PK_Ln |

NOTES:

Non-Standard displays are indicated in the 'IDSL / Example Shell' or 'Programming Notes' column as '[Non-Standard] + Reference.'

11.10.3. Deliverables

| Delivery [Priority] [1] | Description |
|-------------------------|--|
| DS [X] | During Study |
| DE [X] | Dose Escalation |
| IA SAC [X] | Interim Analysis Statistical Analysis Complete |
| SAC [X] | Final Statistical Analysis Complete |

NOTES:

1. Indicates priority (i.e. order) in which displays will be generated for the reporting effort

11.10.4. Study Population Tables

| Study | Study Population Tables | | | | | |
|--------|---|-------------------------|--|---|---------------------------|--|
| No. | Population | IDSL / Example Shell | Title | Programming Notes | Deliverable [Priority] | |
| Subjec | t Disposition | | | | | |
| 1.1. | Safety | ES1 | Summary of Participant Disposition – Part 1 | The general layout of all the study population tables would follow mock shell SAFE_T1 for the column headers and order for both Part 1 and Part 2 tables. | SAC | |
| | | | | This will not include Cohort C, Part 1. | | |
| 1.2. | Safety | ES1 | Summary of Participant Disposition – Part 2 | | SAC | |
| 1.3. | Bystander Safety (Part 1, Cohort C) | ES1 | Summary of Participant Disposition – Bystander | Only for Cohort C, Part 1. | SAC | |
| 1.4. | All Participants Screened) | ES6 | Summary of Screening Status and Reasons for Screen Failure – Part 1 | This will not include Cohort C, Part 1. | SAC | |
| 1.5. | All Participants Screened | ES6 | Summary of Screening Status and Reasons for Screen Failure – Part 2 | | SAC | |
| 1.6. | All Participants Screened | ES6 | Summary of Screening Status and Reasons for Screen Failure – Bystander | Only for Cohort C, Part 1. | SAC | |
| Protoc | ol Deviation | | | | | |
| 1.7. | Safety | DV1 | Summary of Important Protocol Deviations – Part 1 | This will not include Cohort C, Part 1. | SAC | |
| 1.8. | Safety | DV1 | Summary of Important Protocol Deviations – Part 2 | | SAC | |

| Study I | Study Population Tables | | | | | |
|---------|---|-------------------------|---|---|---------------------------|--|
| No. | Population | IDSL / Example Shell | Title | Programming Notes | Deliverable [Priority] | |
| 1.9. | Bystander Safety (Part 1, Cohort C) | DV1 | Summary of Important Protocol Deviations - Bystander | Only for Cohort C, Part 1. | SAC | |
| Popula | tion Analysed | | | | • | |
| 1.10. | All Screened | SP1A | Summary of Study Populations – Part 1 | | SAC | |
| 1.11. | All Screened | SP1A | Summary of Study Populations – Part 2 | | SAC | |
| 1.12. | Bystander Safety (Part 1, Cohort C) | SP1A | Summary of Study Populations – Bystander | Only for Cohort C, Part 1. | SAC | |
| Demog | raphic and Bas | eline Characteris | tics | • | | |
| 1.13. | Safety | DM1 | Summary of Demographic Characteristics – Part 1 | This will not include Cohort C, Part 1. | SAC | |
| 1.14. | Safety | DM1 | Summary of Demographic Characteristics – Part 2 | | SAC | |
| 1.15. | Bystander Safety (Part 1, Cohort C) | DM1 | Summary of Demographic Characteristics – Bystander | Only for Cohort C, Part 1. | SAC | |
| 1.16. | Safety | DM5 | Summary of Race and Racial Combinations – Part 1 | This will not include Cohort C, Part 1. | SAC | |
| 1.17. | Safety (Part 2) | DM5 | Summary of Race and Racial Combinations – Part 2 | | SAC | |
| 1.18. | Bystander Safety (Part 1, Cohort C) | DM5 | Summary of Race and Racial Combinations – Bystander | Only for Cohort C, Part 1. | SAC | |
| 1.19. | Safety | DM6 | Summary of Race and Racial Combination Details – Part 1 | This will not include Cohort C, Part 1. | SAC | |
| 1.20. | Safety (Part 2) | DM6 | Summary of Race and Racial Combination Details – Part 2 | | SAC | |

| Study | Study Population Tables | | | | |
|-------|---|-------------------------|--|---|---------------------------|
| No. | Population | IDSL / Example Shell | Title | Programming Notes | Deliverable [Priority] |
| 1.21. | Bystander Safety (Part 1, Cohort C) | DM6 | Summary of Race and Racial Combination Details – Bystander | Only for Cohort C, Part 1. | SAC |
| 1.22. | Enrolled | DM11 | Summary of Age Ranges – Part 1 | This will not include Cohort C, Part 1. Please include the footnote: "[1] Age is calculated based on screening date, using date of birth, truncated to integer value. Note that only the year of birth has been collected where the day and month would be 30th June for all subjects." | SAC |
| 1.23. | Enrolled | DM11 | Summary of Age Ranges – Part 2 | Please include the footnote: "[1] Age is calculated based on screening date, using date of birth, truncated to integer value. Note that only the year of birth has been collected where the day and month would be 30th June for all subjects." | SAC |
| 1.24. | Enrolled | DM11 | Summary of Age Ranges – Bystander | Only for Cohort C, Part 1. Please include the footnote: "[1] Age is calculated based on screening date, using date of birth, truncated to integer value. Note that only the year of birth has been collected where the day and month would be 30th June for all subjects." | SAC |

| Study I | Population Tabl | les | | | |
|---------|---|-------------------------|---|---|---------------------------|
| No. | Population | IDSL / Example Shell | Title | Programming Notes | Deliverable [Priority] |
| Prior a | nd Concomitan | t Medications | | | |
| 1.25. | Safety | MH1 | Summary of [Current/Past] Medical Conditions – Part 1 | This will not include Cohort C, Part 1. | SAC |
| 1.26. | Safety | MH1 | Summary of [Current/Past] Medical Conditions – Part 2 | | SAC |
| 1.27. | Bystander Safety (Part 1, Cohort C) | MH1 | Summary of [Current/Past] Medical Conditions - Bystander | Only for Cohort C, Part 1. | SAC |
| 1.28. | Safety | CM1 | Summary of Concomitant Medications – Part 1 | This will not include Cohort C, Part 1. | SAC |
| 1.29. | Safety | CM1 | Summary of Concomitant Medications – Part 2 | | SAC |
| 1.30. | Bystander Safety (Part 1, Cohort C) | CM1 | Summary of Concomitant Medications – Bystander | Only for Cohort C, Part 1. | SAC |
| 1.31. | Safety | NS1 | Summary of Number of Subjects by Country and Site ID - Part 1 | This will not include Cohort C, Part 1. | SAC |
| 1.32. | Safety | NS1 | Summary of Number of Subjects by Country and Site ID - Part 2 | | SAC |
| 1.33. | Bystander Safety (Part 1, Cohort C) | NS1 | Summary of Number of Subjects by Country and Site ID - Bystander | Only for Cohort C, Part 1. | SAC |

